6.4 End of Treatment/Early Termination (Visit 10)

The treatment period will be completed at Visit 10. The following activities and/or examinations will be performed at the end of treatment/early termination.

- Collect and review electronic patient diary data, and collecting electronic diary
- Complete SF-MPQ
- Complete the modified BPI-SF
- Complete PGIC
- Complete MOS sleep scale
- Complete HADS
- Complete SF-36
- Complete Evaluation of Symptoms
- Measure body weight
- Perform physical examination
- Perform evaluation of edema
- Perform full neurological examination
- Perform ophthalmologic examination
- Measure blood pressure and pulse rate
- Perform 12-lead ECG
- Collect blood and urine samples for laboratory tests
- Collect blood sample for evaluation of HbA1c
- Collect blood sample for evaluation of fasting blood glucose levels
- Complete C-SSRS
- Perform pregnancy test (only in women of childbearing potential)
- Evaluate AEs
- Record and evaluate concomitant drugs and concomitant therapy
- Collect unused investigational product, and record and review drug-taking compliance

- Record the date of the last dose taken
- Collect blood sample for PK analysis

6.5 Post-treatment Follow-up (Visit 11, 7 days after the completion of administration)

Follow-up observations will be conducted 7 days after the completion of administration (Visit 11). The following activities and/or examinations will be performed at post-treatment follow-up. No follow-up observation is required for subjects enrolled in an open-label extension study.

- Complete HADS
- Measure body weight
- Perform physical examination
- Perform abbreviated neurological examination
- Measure blood pressure and pulse rate
- Collect blood and urine samples for laboratory tests
- Evaluate AEs
- Complete C-SSRS
- Record and evaluate concomitant drugs and concomitant therapy

7. EFFICACY ASSESSMENTS

7.1 Primary Efficacy Variable(s)

Pain score⁷

Each subject will record a pain score in the electronic patient diary once daily from the day after Visit 1 through Visit 10. Every morning upon awakening, prior to taking study medication, the subject will select the number that best describes his or her pain over the past 24 hours on a scale of 0 (no pain) to 10 (worst possible pain). ADPS is the weekly average pain score based on the pain scores from the electronic patient daily pain diaries.

7.2 Secondary Efficacy Variable(s)

1) Response rate

Response rate is defined as the proportion of subjects with $\geq 30\%$, and $\geq 50\%$ reduction from baseline in ADPS.

2) Short-Form McGill Pain Questionnaire⁸

At Visit 1, Visit 2, Visit 3, Visit 4, Visit 5, Visit 6, Visit 7, Visit 8, Visit 9, and Visit 10, subjects will provide a self-assessment using the SF-MPQ. The SF-MPQ consists of 3 parts:

- Fifteen pain descriptors that are given a score of 0 (none) to 3 (severe) based on intensity. The scores are summarized as a sensory score of 11 descriptors, an affective score of 4 descriptors, and a total score of 15 descriptors.
- A VAS, in which the subject rates pain intensity on a 100 mm-long horizontal line, where 0 mm = no pain and 100 mm = worst possible pain.
- A Present Pain Intensity index that provides a score of 0 to 5 based on intensity

3) Modified Brief Pain Inventory (Short Form)⁹

At Visit 2 and Visit 10, subjects will provide a self-assessment using the modified BPI-SF. The modified BPI-SF will be used to assess the severity of pain and the impact of pain on daily function. Subjects will select the number that most closely represents their pain experience on an 11-point scale in two categories: severity, scored from 0 (no pain) to 10 (pain as bad as you can imagine), and impact on daily functions, scored from 0 (does not interfere) to 10 (completely interferes).

Severity of pain

- Worst pain in the last 24 hours

- Least pain in the last 24 hours
- Average pain
- Pain right now

Impact on daily functions

- General activity
- Mood
- Walking ability
- Normal work (includes both work outside the home and housework)
- Relations with other people
- Sleep
- Enjoyment of life

4) Patient Global Impression of Change⁷

At Visit 10, subjects will provide a self-assessment in comparison to Visit 2, using the 7-point scale in the PGIC.

- 1: very much improved
- 2: much improved
- 3: minimally improved
- 4: no change
- 5: minimally worse
- 6: much worse
- 7: very much worse

5) Sleep-interference Score

The Daily Sleep Interference Diary consists of an 11-point NRS which will be used to assess how pain has interfered with the subject's sleep during the past 24 hours. Each subject will record a sleep-interference score in the electronic patient diary once daily from the day after Visit 1 through Visit 10. Every morning upon awakening, prior to taking study medication, the subject will select the number that best describes his or her sleep interference experience during the past 24 hours on a scale of 0 (pain did not interfere with sleep) to 10 (pain completely interfered with sleep). The weekly average sleep interference score is based on the sleep interference scores from the electronic patient daily pain diaries.

6) Medical Outcomes Study sleep scale^{10,11}

At Visit 2 and Visit 10, subjects will provide a self-assessment using the MOS sleep scale. The MOS sleep scale is based on questions about sleep quality during the past 4 weeks, and consists of 3 parts:

- The average time required to fall asleep
 - 0-15 minutes.....1
 - 16-30 minutes.....2
 - 31-45 minutes.....3
 - 46-60 minutes.....4
 - More than 60 minutes.....5
- The average hours of sleep per night, given as number of hours per night.
- 10 questions that are given a score of 1 (all of the time) to 5 (none of the time), based on sleep disturbance in the following areas: difficulty in falling asleep or remaining asleep, difficulty in staying awake during the day, difficulty in breathing, and snoring during sleep.

7) Hospital Anxiety and Depression Scale¹²

At Visit 2 and Visit 10, subjects will provide a self-assessment using the HADS, which will be adopted as efficacy evaluation. The HADS consists of 7 items to score depression (4-point scale) and 7 items to score anxiety (4-point scale). The subject will respond to each item on the questionnaire.

8) SF-36¹³

At Visit 2 and Visit 10, subjects will provide a self-assessment using the SF-36. The SF-36 questionnaire yields an 8-scale profile of the subject's self-assessed QOL in the following categories: Physical Functioning (3-point scale, 10 items), Role-Physical (5-point scale, 4 items to score role limitations caused by physical problems), Bodily Pain (6-point scale, 1 item; 5-point scale, 1 item), General Perception of Health (5-point scale, 5 items), Vitality (5-point scale, 4 items), Social Functioning (5-point scale, 2 items), Role-Emotional (5-point scale, 3 items to score role limitations caused by emotional problems) and Mental Health (5-point scale, 5 items). The subject will respond to each item on the questionnaire.

9) Evaluation of Symptoms⁶

At Visit 10, subjects will provide a self-assessment of “pain excepting ‘tingling’ and ‘pins

and needles' ”, “ ‘tingling’ or ‘pins and needles’ ”, and “dysesthesia” in their feet in comparison to baseline, using the following 4-point scale.

- 1: improved
- 2: no change
- 3: worse
- 4: no symptoms

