6.3 Treatment Period

The treatment period will be 14 weeks in duration.

6.3.1 Visit 3 and Visit 4

From Visit 2 to Visit 4, subjects will come to the study site every week (Visit 3, Visit4). The investigator or sub-investigator will confirm tolerability and review continuation of

the treatment before issuing the new investigational product. The following activities and/or examinations will be performed at Visit 3 and Visit 4.

- Review electronic patient diary data
- Complete SF-MPQ
- Complete HADS
- Measure body weight
- Perform physical examination
- Perform abbreviated neurological examination
- Measure blood pressure and pulse rate
- Collect blood and urine samples for laboratory tests
- Evaluate AEs
- Complete C-SSRS
- Record and evaluate concomitant drugs and concomitant therapy
- Collect unused investigational product, and record and review drug-taking compliance
- Record the date of the first dose taken
- Issue the investigational product
- Collect blood sample for PK analysis

6.3.2 Visit 5, Visit 6, Visit 7, Visit 8, and Visit 9

From Visit 4 to Visit 9, subjects will come to the study site once every 2 weeks (Visit 5, Visit 6, Visit 7, Visit 8, and Visit 9). The investigator or sub-investigator will confirm tolerability and review continuation of the treatment before issuing the new investigational product. The following activities and/or examinations will be performed at Visit 5, Visit 6, Visit 7, Visit 8, and Visit 9.

- Review electronic patient diary data
- Complete SF-MPQ
- Complete HADS
- Measure body weight
- Perform physical examination
- Perform abbreviated neurological examination
- Measure blood pressure and pulse rate
- Collect blood and urine samples for laboratory tests
- Collect blood sample for evaluation of HbA1c (Visit 6 only)
- Collect blood sample for evaluation of fasting blood glucose levels (Visit 6 only)

- Evaluate AEs
- Complete C-SSRS
- Record and evaluate concomitant drugs and concomitant therapy
- Collect unused investigational product, and record and review drug-taking compliance
- Issue the investigational product
- Collect blood sample for PK analysis (Visit 6 and Visit 8 only)

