9.8.4 Hospital Anxiety and Depression Scale¹²

At each visit, subjects will provide a self-assessment using the HADS. The HADS consists of 7 items to score depression (4-point scale) and 7 items to score anxiety (4-point scale). The subject will respond to each item on the questionnaire. Based on the results, the investigator will check for the presence or absence of depression and/or anxiety. If the subject is judged to have an AE, appropriate measures will be implemented such as referring the subject to a specialist. Results will be recorded in the CRF.

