11.5.2 Secondary Efficacy Analyses

Secondary efficacy analyses will be performed using the mITT analysis set. For all secondary endpoints, the summary statistics or frequency tables will be created by treatment group for each week or scheduled visit. The secondary endpoints for each DS-5565 arm will be compared with that for placebo with no adjustment of multiple comparisons.

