11.5.2.7 Hospital Anxiety and Depression Scale

For the subscales of anxiety and depression, the measured value and the change from baseline will be summarized at baseline and Visit 10. The change from baseline in the subscales above will be compared between each arm of DS-5565 and placebo.

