11.7.7 Hospital Anxiety and Depression Scale

The subscales of anxiety and depression for HADS will be summarized at each scheduled visit.

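### HADS is completed at every visit, but the efficacy comparison on mood uses only baseline and Visit 10; a repeated-measures model on the scores already collected would be a cheap improvement

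*Combined protocol and SAP*

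**What the plan says.** **Collection.** Section 9.8.4 (safety): "At each visit, subjects will provide a self-assessment using the HADS". The procedure lists agree. Section 6.3.1 (Visits 3 and 4) and Section 6.3.2 (Visits 5 to 9) each include "Complete HADS".

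**Efficacy use.** Section 7.2, item 7: "At Visit 2 and Visit 10, subjects will provide a self-assessment using the HADS, which will be adopted as efficacy evaluation". Section 11.5.2.7: "For the subscales of anxiety and depression, the measured value and the change from baseline will be summarized at baseline and Visit 10". That section then compares change from baseline between each DS-5565 arm and placebo. It names no model and no rule for missing scores.

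**Safety use.** Section 11.7.7: "The subscales of anxiety and depression for HADS will be summarized at each scheduled visit". Under Section 9.8.4 the investigator also uses each score to check for depression or anxiety.

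**General rule for secondary endpoints.** Section 11.5.2: "For all secondary endpoints, the summary statistics or frequency tables will be created by treatment group for each week or scheduled visit". It adds: "The secondary endpoints for each DS-5565 arm will be compared with that for placebo with no adjustment of multiple comparisons".

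**Early withdrawal.** Sections 4.2.3 and 6.4 ask withdrawn subjects, as far as they cooperate, to complete the Visit 10 assessments, which include HADS. Table 17-1 gives early termination its own column. Nothing says whether such a score enters the efficacy analysis as a Visit 10 value.

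**The concern.** The effect on mood is part of a secondary objective (Section 2.1.2). The plan has eight on-treatment HADS scores per completer and compares arms on one of them. A subject who stops at Week 8 has five scheduled on-treatment scores (Visits 3 to 7). In the efficacy comparison that subject contributes either nothing or a single early-termination score whose status is undefined.

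The restriction is not explained, and it stands apart from the rest of the plan. Section 11.5.2 foresees summaries by week or visit for all secondary endpoints. SF-MPQ, completed at the same treatment visits, is summarised at every one (Section 11.5.2.2). The modified BPI-SF, MOS sleep scale and SF-36 are also compared on two visits, but they are collected only at those two.

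Dropout could plausibly depend on recorded HADS. The investigator acts on the score at each visit when an adverse event is judged present (Section 9.8.4), and difficulty in continuing because of an adverse event is a withdrawal criterion (Section 4.2.1). If that dependence differs by arm, an analysis that ignores the earlier scores can be biased, and one that uses them can correct for it. At stake are a little precision and some protection against dropout bias on one unadjusted secondary endpoint.

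**Working it through.** **Plan's own figure.** None exists for HADS. The only power figures are for ADPS (Table 11-1), and this point does not dispute them. Simulating the Section 11.5.1 procedure with 300 placebo and 150 per active arm, difference 0.6 and SD 1.8 gives 90.3% for each BID arm and 87.7% for 15 mg QD. The first row of the table states 89.5%, 89.3% and 87.0%. The group sizes used below are therefore the plan's.

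**Inputs.** From the documents: 300 placebo and 150 per active arm (Section 11.11), baseline at Visit 2, and eight on-treatment visits (3 to 10), of which seven (3 to 9) are outside the efficacy comparison. Assumed, because the documents give neither: dropout of 0 to 30%, spread evenly after Visits 3 to 9, and HADS correlations between visits (equal at 0.5 or 0.7, or first-order autoregressive at 0.8 or 0.9 per visit).

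**Step 1: precision.** Let C be the covariance of the Visit 3 to 10 scores given baseline, in units of the HADS variance, and d the dropout proportion.

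- Visit 10 observed cases, adjusted for baseline: per-subject variance C₁₀,₁₀ / (1 − d).
- Repeated measures: per-subject variance is the Visit 10 diagonal element of [Σₖ pₖ Cₖ⁻¹ + (1 − d) C⁻¹]⁻¹. Here Cₖ is the block for the visits seen by subjects who leave after visit k, padded with zeros once inverted, and pₖ = d/7.

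Example: equal correlation 0.7, d = 0.2. C₁₀,₁₀ = 1 − 0.7² = 0.51. Observed cases: 0.51/0.8 = 0.6375. The computed variance ratio is 0.942, so the standard error ratio is √0.942 = 0.971, a reduction of 2.9%.

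Change in the standard error of the Visit 10 contrast when Visits 3 to 9 are added:

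| Assumed correlation | 0% dropout | 10% | 20% | 30% |
|---|---|---|---|---|
| Equal, 0.5 | 0 | −1.1% | −2.1% | −3.3% |
| Equal, 0.7 | 0 | −1.4% | −2.9% | −4.5% |
| Autoregressive, 0.8 | 0 | −1.2% | −2.5% | −4.0% |
| Autoregressive, 0.9 | 0 | −1.8% | −3.9% | −6.2% |

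**Step 2: bias.** Simulation with 300 against 150, no true effect, and 1,000 repetitions per row. After each of Visits 3 to 9, log-odds of dropout = −3.5 + slope × current HADS (SD units). With slope 0 the chance per visit is 1/(1 + e^3.5) = 0.0293, so total dropout is 1 − (1 − 0.0293)⁷ = 18.8%. Three analyses, all adjusted for baseline, were compared: Visit 10 observed cases; repeated measures; and the last score before dropout used as Visit 10, standing in for an early-termination score. Negative bias favours the active arm.

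| Slope, placebo / active | Correlation | Dropout, placebo / active | Visit 10 observed | Repeated measures | Last score as Visit 10 |
|---|---|---|---|---|---|
| 0.5 / 0.5 | all three | about 20–21% each | about 0 | about 0 | about 0 |
| 0 / 1.0 | equal 0.5 | 18.8% / 25.9% | −0.069 | −0.002 | +0.115 |
| 0 / 1.0 | equal 0.7 | 18.8% / 25.2% | −0.055 | −0.002 | +0.067 |
| 0 / 1.0 | autoregressive 0.9 | 18.8% / 25.0% | −0.099 | −0.002 | +0.066 |

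In the last three rows the observed-case standard errors are 0.097, 0.079 and 0.102. The bias is thus 0.069/0.097 = 0.7, 0.055/0.079 = 0.7 and 0.099/0.102 = 1.0 standard errors.

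**Step 3: a different mechanism.** Here placebo dropout follows the last HADS score and active dropout does not. Overall dropout is 14 to 20%, the true effect 0.2 SD, with 400 repetitions. Visit 10 observed cases are biased toward no effect by 0.025 to 0.045 SD, and repeated measures is within 0.007 SD of the truth. The Monte Carlo errors of 0.004 to 0.0055 imply standard errors of about 0.08 to 0.11 (× √400), so this bias is roughly 0.2 to 0.6 standard errors.

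The sign changes between Steps 2 and 3 and, within Step 2, between the two ways of handling early termination. Repeated measures stays close to zero bias throughout, because dropout in these simulations depends only on observed scores.

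**The case against.** A reader might infer that the Visit 3 to 9 scores are thrown away. The documents do not support that: Section 11.7.7 summarises them at each visit, and Section 9.8.4 uses them for monitoring. They are missing only from the efficacy comparison.

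A reader might also take the plan to be a completers-only analysis with a known direction of bias. That is not shown either. Section 11.5.2.7 names no model, Section 11.2 leaves detail to a SAP to be written before unblinding, and an early-termination HADS is requested. The Asian Phase 2 adverse-event rates (73.3% at 15 mg BID, 53.4% on placebo) are incidences of events, not discontinuations, and say nothing about whether dropout tracks HADS.

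It is fair, too, that a baseline-to-Visit 10 comparison is a legitimate prespecified endpoint and the one used for three other questionnaires. The pain analogy is also inexact: the primary ADPS analysis imputes under missing not at random, and the observed-data MMRM is only a sensitivity analysis (Section 11.5.1).

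All of this limits the size and certainty of the point but does not remove it. The two-visit restriction is written into the protocol, so it is more than silence awaiting a SAP. Both available readings of how early withdrawals are handled are biased in the arm-differential scenario, in opposite directions.

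**Conclusion.** The point holds as a cheap improvement. The secondary mood comparison leaves out seven on-treatment scores that are collected anyway. There is no general loss of precision: the cost is zero with complete data and about 1 to 6% of the standard error at 10 to 30% dropout. Bias is a risk only if dropout depends on observed HADS differently by arm. It then ranges from a few hundredths to about 0.1 SD in the scenarios tried, with a sign set by the mechanism and by the unstated early-termination rule. It is about zero if dropout follows HADS equally in both arms. Dropout rates, correlations and dropout mechanisms are all assumptions. HADS is a secondary endpoint tested without multiplicity adjustment, so no primary conclusion is affected.

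**What to change.** In Section 7.2, item 7, and Section 11.5.2.7, before unblinding:

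- adopt HADS from Visits 3 to 10 for efficacy, with Visit 2 as baseline;
- analyse each subscale with an MMRM containing treatment, visit, treatment-by-visit, baseline subscale score and baseline-by-visit, and read the treatment difference at Visit 10;
- assign early-termination scores to the scheduled visit nearest in time instead of treating them as Visit 10;
- leave the safety summaries in Section 11.7.7 unchanged.

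The cost is protocol and SAP wording and one model per subscale, with no new data. The small downside is reliance on missing at random, which the observed-data MMRM for ADPS in Section 11.5.1 also makes.

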8. PHARMACOKINETIC AND BIOMARKER ASSESSMENTS

8.1 Pharmacokinetic Variable(s)

Blood samples will be taken at the sites capable of blood sampling. Blood sample will be collected one time each at Treatment Period Visits (Visit 3, Visit 4, Visit 6, and Visit 8) and at End of Treatment/Early Termination Visit (Visit 10). At least one blood sample must be collected within 4 hour after administration. Blood samples will be collected in accordance with the procedures described in Section 17.2. In the CRF, the following will be recorded:

- Administration/No administration in the morning on the day before each visit
- Administration/No administration at bedtime on the day before each visit
- Administration/No administration in the morning on the day of each visit
- Date/Time of the morning dose on the day before each visit
- Date/Time of the bedtime dose on the day before each visit
- Date/Time of the morning dose on the day of each visit
- Taking/No taking breakfast on the day of each visit
- Date/Time of breakfast on the day of each visit
- Date/Time of blood sampling

Although PK samples will be taken for all subjects, drug concentration will be measured only on subjects receiving DS-5565.

8.2 Biomarker Variable(s)

No biomarker analysis will be performed.

9. SAFETY ASSESSMENTS

Safety endpoints will be body weight, AEs, laboratory values, vital signs, 12-lead ECG, findings from physical examination, findings from neurological examination, C-SSRS, HADS, edema, and findings from ophthalmologic examination.

9.1 Adverse Events

9.1.1 Definition of Adverse Event

An AE is any unfavorable and unintended sign (including an abnormal laboratory value or abnormal vital sign), symptom, or disease that develops after the subject signs the Informed Consent Form (ICF) and up to 7 days after the last dose of study medication (Visit 11), regardless of relationship to the investigational product.

Any symptom that the investigator or sub-investigator considers associated with DPN will be evaluated as an efficacy variable and will not be regarded as an AE. However, if the symptom is considered potentially related to the investigational product, such symptom will be regarded as an AE. If any pre-existing symptom or disease is aggravated during the study period, the aggravation will be reported as an AE, and the date of confirming the aggravation will be considered the date of event onset.

Dizziness, somnolence, edema, and weight increase are currently defined as “significant AEs”. Any other significant AEs to be added will be specified in the statistical analysis plan (SAP).

All antiepileptic drugs carry a risk of increased suicidal behavior and ideation. Furthermore, increased hepatic transaminases have been observed in the DS-5565 development program. Therefore, the following “suicidal behavior and ideation” and “liver enzyme elevations/liver dysfunction” will be treated as adverse events of special interest.

- Increase in ALT or AST ≥ 5 x ULN
- ALT or AST rises to ≥ 3 x ULN and persists for more than 2 weeks
- Concurrent increases in ALT or AST ≥ 3 x ULN and T-Bil ≥ 2 x ULN
- ALT or AST ≥ 3 x ULN associated with a clinical presentation suggestive of liver injury (ie, including the appearance of fatigue, nausea, vomiting, jaundice, right upper quadrant pain or tenderness, fever, rash, and/or eosinophilia)
- Serious hepatobiliary adverse event
- Severe hepatobiliary adverse event

- Hepatobiliary Adverse event leading to Discontinuation
- Any transaminase elevation associated with a clinical presentation suggestive of Liver injury
- An elevation of ALT or AST $\geq 3 \times$ ULN (without clinical presentation suggestive of liver injury)
- AE related to suicide (if there are any “yes” responses to any of the questions in the C-SSRS)

